#### **Study Procedures**

#### 1. Sample Grouping

This study will comprise two equal groups of converted dentures based on their fabrication techniques in pateintes rehabilitated with a full arch implant supported prosthesis as follows:

**Group I**: fifteen dentures were converted conventially to be used as a fixed interim prosthesis for immediate loading.

**Group II**: fifteen dentures were converted digitally to be used as a fixed interim prosthesis for immediate loading.

#### 2. Patient selection

Thirty patients will be selected from the outpatient clinic of the Oral and Maxillofacial Prosthodontics Department, Faculty of Dentistry, Ain Shams

#### • Inclusion criteria

-Nonsmokers

-Free from any systemic disease

-Non-bruxers

-With sufficient quality and quantity of bone

-Prepared to comply with the follow-up and maintenance program

#### • Exclusion criteria

- Patients with bad oral hygiene.
- Patients with limited mouth opening.
- Vulnerable groups.
- Uncooperative patients.

#### • Patient evaluation

#### * History

Precise medical and dental history will be taken from all patients.

#### * Examination

Comprehensive extraoral and intraoral examinations will be carried out to verify patients fulfilling the selection criteria.

## 3. Clinical and Laboratory Procedures

For both groups, multiunit abutments will be inserted for each implant and secured to them according to the recommended torque. A small amount of putty rubber base will be mixed and

placed into the fitting surface of the pre-treatment denture, which then will be seated intraorally to mark the sites of the multiunit abutments. The denture will then be relieved over the marked sites until it was fully seated without interference.

For group I a conventional denture conversion will be made. For group II; the denture will be scanned extraorally using intraoral scanner. An intra oral scan will be made for the ridge form and multiunit abutments scan bodies and the scan will be extended to include the buccal and labial aspect of the ridge following the continuous scanning strategy.⁸

A scan of the opposing arch will be done then a large vent hole will be drilled in the denture, removing a portion of the flange and anterior teeth while maintaining the integrity of the lingual / palatal aspect to connect to the other side base and teeth. The denture will be inserted intraorally and the patient will be instructed to bite in centric occlusion to make an intra oral bite scan which records the exposed area of the ridge, the opposing arch, and the remaining portion of the denture. Alignment of scans will be done on Medit compare application. These scans will be exported to the design software and alignment will be done by a software as well, virtual alignment of all scans to each other will be performed except for the denture scan which will be loaded separately as a pre-operative wax up. On the aligned scans, multi-unit abutments scan bodies will be matched to the digital library scan bodies and virtual multiunit abutment analogues will be generated then, titanium sleeves abutments will be selected. Alignment of denture scan. Design of virtual gingiva will be made with flat fitting surface without overhangs or ridge lap parts. The screw access holes will be aligned and the area surrounding these channels will be thickened.

The STL file will be exported for millin from shaded PMMA disc A 3.5. After milling, the gingival portions will be coated with pink or red resins, NextDent Base and curing will be done. Titanium sleeve abutments will be cemented with the proper length to their respective sites with resin cement and cured. The interim fixed PMMA bridge will be delivered intra orally by sequential screwing of the prosthetic screws after verification of the seating and the proper tissue contact. Occlusion will be checked and equalised intraorally to establish centric balance with the opposing arch. Then the prosthetic screws will be torqued, and screw access holes will be sealed with flowable resin.

# 4. Methods of Evaluation

General satisfaction, chair side working time, and esthetic outcome of the prostheses were recorded and quantified with a verbal rating scale following insertion of implant-supported prosthesis.

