#### **Materials and Methods**

After intra oral scanning of the ridge form, implant positions, the denture is used to scan the intermaxillary relation and tooth positions and the fixed interim is designed and milled from PMMA. This technique is applicable when a single arch is treated or for bimaxillary implant rehabilitation cases. In this study 30 patients were grouped into two groups; group I in which a converted denture was made conventionally and Group II in which a converted denture was made digitally. General satisfaction, chair side working time, and esthetic outcome of the prostheses were recorded and quantified with a verbal rating scale following insertion of implant-supported prosthesis.

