# **III. Research Question**

Will the digital conversion of the pre-treatment complete dentures in immediately loaded full arch implant cases, introduce a more time saving solution and better patient satisfaction?

Problem	the conventional denture conversion technique					
	is troublesome for both practitioner and the					
	patient					
Intervention	An alternative workflow for construction of					
	the fixed interim requires impressions, model					
	production, and jaw relation records then					
	digitizing all these data then designing and					
	milling the restoration.					
Comparator	A conventional denture conversion will be					
	done following the conventional fabrication					
	technique.					
Outcome	General satisfaction, chair side working time,					
	and esthetic outcome of the prostheses with a					
	verbal rating scale following insertion of					
	implant-supported prosthesis.					
Time of Follow-up	One week for fabrication of the denture					
	digitally, but no follow-up is needed.					
Study Settings	Removable Prosthodontics Department,					
	Faculty of Dentistry, Ain Shams University.					

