#### IV. Aim of the Study Outcomes and Clinical Relevance

#### Aim

The objective of this study is to find out if a digitalised workflow will be time and cost effective when converting the pre-treatment complete denture into a screw retained immediately loaded full arch implant supported bridge.

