#### Outcome

General satisfaction, chair side working time, and esthetic outcome of the prostheses with a verbal rating scale following insertion of implant-supported prosthesis.

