# Questionnaire about patient satisfaction level with different techniques of denture conversion:

	Questions	0	1	2	3	4	5
1	How do you feel about the pleasure you get from food compared to						
	your complete denture?						
2	With respect to appearance, how satisfied are you with your fixed						
	restoration in comparison to your denture?						
3	With respect to speech, are you satisfied with your current fixed						
	prosthesis?						
4	How comfortable were you during the process of denture fixation?						
5	With respect to time, how satisfied are you with the process of						
	denture fixation?						

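### The aim is saving of time and cost, but chair-side time has no unit or timing method and reads most naturally as a rating, and cost is not measured at all

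*Protocol*

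**What the plan says.** The Aim section of the Protocol states: "The objective of this study is to find out if a digitalised workflow will be time and cost effective". The Research Question asks whether digital conversion will "introduce a more time saving solution and better patient satisfaction".

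Chair-side working time is then named in four places:

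- Abstract, Materials and Methods: satisfaction, chair-side time and esthetic outcome "were recorded and quantified with a verbal rating scale following insertion of implant-supported prosthesis".
- Research Question table, Outcome row: the row begins "General satisfaction, chair side working time", adds esthetic outcome, and ends with a "verbal rating scale following insertion of" the prosthesis.
- Outcome: general satisfaction, "chair side working time, and esthetic outcome of the prostheses with a verbal rating scale".
- Methods of Evaluation: "chair side working time, and esthetic outcome of the prostheses were recorded and quantified with a verbal rating scale".

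The questionnaire has five items scored 0 to 5. Item 5 is the only one on time: "With respect to time, how satisfied are you with the process of" fixing the denture.

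The Hypothesis section has one null hypothesis, on patient satisfaction. Cost effectiveness appears in the Background as an expectation and in the Aim as the objective. The Research Question table also allows one week for digital fabrication, and the Ethical Considerations list a saving of time for dentist and patient among the benefits.

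**The concern.** An aim about saving time needs a duration, and an aim about cost needs a cost. The Protocol does not leave the measurement of time open for another document: it states a rule, and on its most natural reading that rule turns a duration into a rating. A statistical analysis plan cannot repair this, because it can only analyse data that the Protocol has collected.

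Satisfaction with time is also a different quantity from time. A patient in the digital group might spend fewer minutes in the chair, wait a week for the milled bridge, and rate the time poorly; the reverse could happen in the conventional group. A patient's rating also says nothing about the dentist's time, which the Ethical Considerations expect to be saved.

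What is at stake is the conclusion. The Background already expects the digital workflow to be efficient in time and cost. If only ratings exist, a report that it proved so would rest on a satisfaction score, and the expectation would remain untested.

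**Working it through.** The point turns on wording, not on a calculated figure. For completeness, the planned sample size does reproduce. With d = 1.050, two-sided alpha 0.05 and 80% power, the normal approximation gives n = 2 × (1.960 + 0.842)² / 1.050² = 15.70 / 1.1025 = 14.24, so 15 per group and 30 in total. This does not help here, because the Sample Size Calculation does not say which outcome the effect size belongs to.

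**Step 1: what the aim needs.** The Aim needs a time measure and a cost measure. The Research Question needs a time measure and a satisfaction measure.

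**Step 2: how chair-side time is measured.** All four places that name it also name a verbal rating scale, but they do not carry equal weight:

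| Place | Wording | Reading |
|---|---|---|
| Abstract, Materials and Methods | three outcomes share one verb phrase | scale most naturally covers all three |
| Methods of Evaluation | same sentence | scale most naturally covers all three |
| Research Question, Outcome row | list, no verb | scale may cover all three or esthetic outcome only |
| Outcome | list, no verb | scale may cover all three or esthetic outcome only |

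These are repetitions of one sentence, not four separate rules. None of them, and no other section, gives minutes, a clock, start and stop events, or a person who does the timing.

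**Step 3: whether the instrument fills the gap.** Of the 5 questionnaire items, 0 record a duration, 0 record a cost, and 1 (item 5) asks for satisfaction with time. Item 5 refers to the process of fixing the denture, not specifically to chair-side work.

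**Step 4: cost.** It is named in two places (Background and Aim). No outcome, questionnaire item, procedure or analysis collects it. The Funding section concerns only who pays for the study.

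**Step 5: what chair-side time would have to contain.** Under Clinical and Laboratory Procedures, group II goes through scanning at the chair, then software design, milling, coating and curing, then delivery at the chair. One start-to-stop interval would therefore include laboratory work. Chair-side time in group II must be a sum of at least two segments, scanning and delivery. That sum in turn leaves out the week allowed for digital fabrication, so it cannot by itself show a saving in total time.

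**Step 6: what can be answered.**

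| Question | As written |
|---|---|
| Better patient satisfaction | yes |
| Satisfaction with time | yes, item 5 |
| Time saving | no, unless unmentioned minutes exist |
| Cost effectiveness | no, on any reading |

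**The case against.** The strongest reply is that chair-side working time names a duration, that the verb used in the Abstract and in Methods of Evaluation includes recording as well as rating, and that in the other two places the scale can belong to esthetic outcome alone. Minutes may then have been taken, and the fault would be a badly built sentence. This stands in part. A reader might infer from four matching passages that the Protocol proves elapsed time was never measured. It does not: the passages repeat one sentence, two of them are ambiguous, and the document does not show whether minutes were recorded. What remains is that no unit or timing method is stated anywhere, and that the operative section reads most naturally as a rating.

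A second reply is that cost is a stray word. It is absent from the Research Question, the Outcome section and the Hypothesis, and deleting it from the Aim settles the matter. That is true of the remedy, but the Aim still contains it.

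A third is that the only hypothesis concerns satisfaction, which can be tested. That also stands, and it limits the point: a reader who concluded that the trial can answer nothing would go too far. Which endpoint is primary is a separate question that a statistical analysis plan may settle.

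**Conclusion.** The concern holds in a conditional form for time and without condition for cost. On the assumption that no minutes were recorded beyond what the Protocol describes, the trial yields no estimate of chair-side time saved, and neither the time part of the Aim nor the time-saving half of the Research Question can be answered. If minutes were recorded, the time defect shrinks to an omission that one statement in Methods of Evaluation can correct. The cost part of the Aim is unanswerable either way, since nothing collects cost. The satisfaction half of the Research Question and the stated null hypothesis are not affected.

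This should be corrected before results are reported, because the objective as worded invites a conclusion that the described data cannot support.

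**What to change.** 1. In the Abstract, the Outcome row of the Research Question table, the Outcome section and Methods of Evaluation, separate chair-side working time from the rating scale. Record it in minutes as the sum of the chair-side segments (in group II at least scanning and delivery), excluding laboratory design, milling and curing. Define the counted steps comparably for both groups.
2. Report questionnaire item 5 only as satisfaction with time.
3. Reword the Aim to refer to chair-side time, and remove cost unless a cost outcome is collected.
4. Do not claim an overall saving of time, in answer to the Research Question or in the benefits under Ethical Considerations, from chair-side minutes alone. Otherwise report total time to delivery as well, so that the week of digital fabrication is counted.
5. Add chair-side time to the Hypothesis, or label the time comparison secondary or exploratory. The label is the simpler course, since the planned effect size is not tied to time.
6. If minutes were already recorded, say so in Methods of Evaluation. If treatment is complete and they were not, restrict the Aim, the Research Question and the conclusions to satisfaction, including satisfaction with time.

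The Mann-Whitney test and the median with interquartile range can be applied to minutes as they are to ratings. The cost is a few timing entries per patient. With at least two segments for each of 15 group II patients and at least one for each of 15 group I patients, that is at least 2 × 15 + 1 × 15 = 45 entries, plus the wording changes. The price is a narrower claim on time and, most likely, none on cost.

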# Questionnaire about patient satisfaction level with different techniques of denture conversion:

	Questions	0	1	2	3	4	5
1	How do you feel about the pleasure you get from food compared to						
	your complete denture?						
2	With respect to appearance, how satisfied are you with your fixed						
	restoration in comparison to your denture?						
3	With respect to speech, are you satisfied with your current fixed						
	prosthesis?						
4	How comfortable were you during the process of denture fixation?						
5	With respect to time, how satisfied are you with the process of						
	denture fixation?						

## **IV. Data Management**

The data will first be recorded manually and then transferred into digital form. The obtained data will be stored in the Oral and Maxillofacial Prosthodontics Department, Ain Shams University library.

# V. Statistical Analysis

The obtained data will be recorded, tabulated, and statistically analyzed using the Mann-Whitney U Test was used for comparison between the two groups. Statistics was done with IBM SPSS statistics v20. Data was presented as median and interquartile range.

#### **VI.** Funding

This study will be self-funded.

